16.9 Handling and reporting of adverse events

Investigator will report “*to the sponsor, without unjustified delay, all serious adverse events and device deficiencies that could have led to a serious adverse device effect; this information shall be promptly followed by detailed written reports*” [ISO 14155 § 9.8 b].

All Serious Adverse Events and all Adverse Device Effects (serious or non-serious) are to be documented and reported to the sponsor within a maximum period of 72 calendar hours after becoming aware of the event. Investigator will send reports via EDC, email or fax.

Sponsor contact information:

Non-Serious Adverse Events documentation and reporting are limited to cardiovascular events. These events are to be reported to the sponsor within maximum 10 calendar days after becoming aware of the event.

Where possible, Investigator will return the device involved in the deficiency to Sponsor for analysis.

Investigator will document all AEs on the Adverse Event Form, including (at a minimum) a description of the event, date of onset, severity, relationship to the investigational device and/or procedure, required interventions, duration, and outcome. Investigator will monitor all AEs until they are resolved, determined to be a chronic condition at the last follow-up visit or the subject is lost to follow-up. Investigator will report all AEs regardless of whether it is anticipated or unanticipated and regardless of classification, seriousness, intensity, outcome or causality within 72 calendar hours. Investigator will make all efforts to provide source documentation related to the event (e.g. hospitalization report, medical report, etc.).

In the event of subject death, Investigator will make reasonable effort to obtain a copy of the autopsy report and/or death summary. Investigator will determine the cause of death and its relationship to the investigational device; Investigator will record results on the Adverse Event Form. Investigator will include copies of an autopsy report, if available, and/or a death summary with this form.

Investigator is responsible for reporting all SAEs or SADEs to the EC, according to national regulations and EC requirements. Investigator will forward a copy of this report to Sponsor and file in site regulatory binder.

Sponsor is responsible for classification and reporting of adverse events and ongoing safety evaluation of the clinical investigation in line with ISO 14155:2011 and regulatory requirements.

Sponsor will assure reporting of all SAEs to the Competent Authorities in accordance with European Medical Devices Directives and all applicable national regulations.

17 DATA AND SAFETY MONITORING BOARD

Data Safety Monitoring Board will be responsible for review of data on a periodic basis until 300 patients needed for the PMCF requirements complete 6 months of follow-up.

18 VULNERABLE POPULATION

“Clinical investigations shall be conducted in vulnerable populations only when they cannot be carried out in non-vulnerable populations and shall follow the additional EC procedures where applicable. These clinical investigations shall be designed specifically to address health problems that occur in the vulnerable population, and offer the possibility of direct health-related benefit to the vulnerable population.” § 4.6 ISO 14155:2011

Sponsor and Investigator will exclude vulnerable populations from this clinical study.

19 SUSPENSION OR PREMATURE TERMINATION OF THE CLINICAL STUDY

19.1 Subject lost to follow-up

Investigator will attempt to contact a subject at least three times prior to designating them as lost-to-follow-up subjects; two of these attempts should include attempting to contact subject via registered mail. Investigator will document the date and type of attempted communication. Investigator will complete and sign the Study Withdrawal Form when a subject is lost to follow-up.

19.2 Subject withdrawals and discontinuation

Subjects have the right to withdraw from the clinical study at any time and for any reason without prejudice to their future medical care by the study team or study site. Investigator will ask reason for their withdrawal. Investigator will record all information regarding the subject discontinuation.

A subject may be withdrawn from the clinical study for the following reasons:

- Subjects may choose to withdraw from the clinical study under the terms of the Declaration of Helsinki and their consent documentation without having to give a reason;
- Any unanticipated adverse reaction which is, in the opinion of the Investigator, related to the treatment and will endanger the well-being of the subject if treatment is continued;
- Development of any intercurrent illness(es), infection or condition(s) that might interfere with the CIP;
- Non-compliance with the clinical study procedures deemed by the Investigator to be sufficient to cause discontinuation;

- Any problem deemed by the Investigator to be sufficient to cause discontinuation.

Investigator will treat all subjects discontinued from the study due to an unanticipated adverse reaction, directly related to the study, until the reaction resolves.

Investigator will not replace subjects who have withdrawn from the clinical study if they have received study treatment. If possible, Investigator will perform any procedures or assessments planned for the subject at the time of withdrawal.

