3 STUDY SYNOPSIS

Title	Nanostim study for a leadless cardiac pacemaker system – the LEADLESS observational study
Study Device	Leadless cardiac pacemaker (LCP) system
Regulatory Classification of the Study Device	Active Implantable Medical Device (AIMD) 90/385/EEC.
Study Objective	
To confirm clinical performance and safety of the Nanostim leadless cardiac pacemaker system, within its intended use and according to its instructions for use, by confirming the acceptability of identified risks and detecting emerging risks on the basis of factual evidence.
 
A sub-set of patients enrolled in this study will be used to meet the Post Market Clinical Follow-Up (PMCF) requirement for CE mark. Once this sub-set of patients is enrolled and followed for 6 months, a report will be submitted indicating completion of this requirement.

Number of Institutions	Up to 100 study sites. 
Number of Subjects	A total of 1000 patients will be enrolled. The PMCF will be complete when data from 300 patients followed for 6 months are obtained.
Study Population	Subjects who are at least 18 years old, and who are indicated for a VVI(R) pacemaker Subjects who participated in the pre-CE mark LEADLESS study, in the Nanostim Delivery Catheter pre-CE mark study or were implanted with a Nanostim Leadless Cardiac Pacemaker within 3 months of the study start at one of the selected sites involving physician trainers and study leaders can be enrolled in this study. 

The LEADLESS Observational Study

Schedule of Assessments	
Enrollment, Implant, Pre-discharge, 90-day, 6-month and every 6-month follow-ups thereafter (until the last enrolled subject has completed a 5-year follow-up visit).
 
The PMCF requirement will be met when the 300th patient has completed the 6 month follow-up visit.

Study Design	Prospective, non-randomized, single-arm, multicenter, post-market study
Primary Endpoint	The primary safety endpoint is to evaluate a 180-day complication-free rate, where a complication is defined as a serious adverse device effect (SADE).
Additional Data	
- Pacing and sensing performance- All adverse events- Implant success rate- Procedure time- Time to discharge

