9.3.3 Study duration

The minimum length of the clinical study for each subject will be 5 years. The PMCF requirement will be met when 300 subjects have completed 6 months of follow-up. Subjects will be required to return for follow-up at 90 days (+/- 1 month), 6 months (+/- 1 month) and every 6 months thereafter (+/- 2 months) until the last enrolled subject has completed a 5-year follow-up visit.

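### Section 19.2 lets investigators withdraw implanted subjects from the study for risk-related reasons and provides no later safety data, which could bias the 5-year complication-free rate upward

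*Combined protocol and SAP*

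**What the plan says.** Section 19.2 opens its list with "A subject may be withdrawn from the clinical study for the following reasons". The wording is permissive, and what ends is study participation. Besides the subject's own choice and non-compliance, the listed reasons include:

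- where continuing treatment is the source of the danger, "Any unanticipated adverse reaction which is, in the opinion of the Investigator, related to the treatment and will endanger the well-being of the subject";
- "Development of any intercurrent illness(es), infection or condition(s) that might interfere with the CIP";
- "Any problem deemed by the Investigator to be sufficient to cause discontinuation".

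Implanted subjects are not exempt. On data at exit, the section says "If possible, Investigator will perform any procedures or assessments planned for the subject at the time of withdrawal". It also has the investigator treat an unanticipated reaction until it resolves. Section 16.9 adds that adverse events are monitored until they resolve, are judged chronic at the last visit, or the subject is lost.

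On intended follow-up, section 9.3.3 states "The minimum length of the clinical study for each subject will be 5 years", and section 9.3.4 says that everyone is followed for at least 5 years after implant. The synopsis gives the objective as confirming performance and safety "by confirming the acceptability of identified risks and detecting emerging risks on the basis of factual evidence". Section 6.3 tests 5-year freedom from complications against 75% at a one-sided 5% level; a complication is a SADE.

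Section 10.2, whose title covers loss to follow-up and dropouts, refers to the contact procedure in section 19.1. Its readable text gives no rule for censoring or missing data. Section 9.1.4 says that the sample size allows for dropouts but gives no rate. The sample-size text of section 6.1 is redacted.

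**The concern.** The reasons in section 19.2 read like those of a trial in which treatment ends when the subject leaves. Here the treatment is a device in the right ventricle. Leaving the study does not remove it, so exposure and SADE risk can continue unobserved. Removal or deactivation without a Nanostim replacement is dealt with separately in section 9.4.3.

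Several of the reasons may mark subjects at higher risk. Infection is both a withdrawal reason and an entry in the foreseeable-event list of section 16.8. An unanticipated device-related reaction is the kind of emerging risk that the study is meant to detect, yet it is also a ground for ending observation. If such subjects leave without a recorded SADE and later have one, it is missed. The 5-year comparison with 75% is then made in a group selected for lower risk.

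**Working it through.** **No figure in the plan to reproduce.** The readable text gives no withdrawal rate, no power for the 5-year test and no handling rule for withdrawn subjects. The calculations below therefore show scale only.

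**Inputs from the plan.** Null value 75% and one-sided alpha 5% (section 6.3); N = 1000 enrolled (synopsis).

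**Assumptions.** A fraction w leaves early with no event recorded and is dropped from the analysis. The true 5-year event risk in that group is r. An exact binomial test is used. True freedom in the whole cohort is set at 75%, so any pass is a false pass.

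**Step 1: the test with no withdrawal.** At least 773 of 1000 must be event-free. The exact alpha is 0.049.

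**Step 2: freedom expected among those remaining.**

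S_obs = (0.75 − w(1 − r)) / (1 − w)

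For w = 5% and r = 50%: (0.75 − 0.05 × 0.50) / 0.95 = 0.725 / 0.95 = 76.3%.
For w = 10% and r = 37.5%: (0.75 − 0.10 × 0.625) / 0.90 = 0.6875 / 0.90 = 76.4%.

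**Step 3: chance of wrongly passing.** This is the binomial probability of reaching the required count at S_obs, with n = 1000(1 − w).

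| w | n | Needed | r | S_obs | False-pass rate |
|---|---|---|---|---|---|
| 5% | 950 | 735 | 25% | 75.0% | 4.8% |
| 5% | 950 | 735 | 37.5% | 75.7% | 11.6% |
| 5% | 950 | 735 | 50% | 76.3% | 23.5% |
| 10% | 900 | 697 | 25% | 75.0% | 4.8% |
| 10% | 900 | 697 | 37.5% | 76.4% | 24.1% |
| 10% | 900 | 697 | 50% | 77.8% | 61.3% |

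In the rows with r = 25%, withdrawal is unrelated to risk and the error rate holds. The inflation comes entirely from the link to risk.

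**Step 4: the earlier time points.** Take a constant SADE hazard h with exp(−5h) = 0.77, so h = 0.0523 per year. Withdrawal occurs at rate v per year, and the hazard is k × h after withdrawal. Censoring at withdrawal estimates exp(−ht). True freedom is

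exp(−(h+v)t) + v·exp(−kht)·[exp(((k−1)h − v)t) − 1] / ((k−1)h − v).

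In the worst case tried (v = 3% per year, k = 3), at half a year the estimate is 97.42% and the truth 97.38%, a bias of about 0.04 percentage points. At 5 years the same case gives 77.0% against 74.6%, a bias of 2.4 points. The problem is therefore confined to the long-term endpoint.

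**The case against.** The strongest reply has five parts.

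**Existing safeguards.** A serious device-related reaction or infection is already a SADE and is counted when it occurs. Open adverse events are followed under section 16.9, and withdrawal reasons are asked for and recorded. This stands. It narrows the loss to later events, and to subjects whose problem was not yet a SADE when they left.

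**Permissive wording.** Loss is allowed, not required. This also stands: the bias is a risk created by the rule, not a certainty.

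**No contradiction with section 9.3.3.** A reader might infer that section 19.2 contradicts the 5-year minimum. It does not. A planned duration can coexist with permitted early exit, just as it does with withdrawal of consent. What is missing is provision for data after an investigator-initiated exit.

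**Overstated reach.** A reader might infer that the primary 180-day endpoint is compromised as well. Step 4 shows a bias of about 0.04 points under harsh assumptions. A reader might also infer from an observed 77.0% and a true 74.6% that the study would pass wrongly. It would not on that result: 770 of 1000 gives an exact one-sided p of 0.076, short of the 773 needed. The false-pass rates in step 3 are the proper measure.

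**Assumed inputs.** Neither a withdrawal rate nor a risk after withdrawal appears in the documents, and a handling rule could lie in the redacted part of section 6.1. This limits what can be said about size. However, an allowance for dropouts in the sample size protects precision and does not correct loss that is related to risk.

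**Conclusion.** The point holds for the 5-year supplementary endpoint. As written, section 19.2 allows an implanted subject to leave observation for reasons that may be linked to risk, and the readable text collects no SADE, revision, device status or death arising afterwards.

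The upward direction of the bias depends on withdrawn subjects being at higher risk, which is plausible but not shown in the documents. On the assumptions in step 3, 5-10% withdrawal with 1.5 to 2 times the null event risk (37.5-50% against 25%) raises the nominal 5% error rate to between 12% and 61%. These are illustrations, not forecasts. They treat withdrawn subjects as dropped; the plan does not say how they would be handled. The 90-day and 180-day rates are not materially at issue.

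**What to change.** Amend section 19.2 to separate stopping treatment or study visits from ending data collection.

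- State that an implanted subject who meets an investigator-initiated reason remains in follow-up to 5 years for SADE, revision, device status and vital status, by record review or telephone if visits are not possible. Collection ends earlier only if the subject withdraws consent, dies or is lost to follow-up.
- Reconcile this with section 9.4.3, which limits adverse event assessment to 30 days after removal or deactivation without a Nanostim replacement.
- Report all early exits by reason.
- In section 10.2, state how subjects who still leave early are handled in the 5-year analysis, with a sensitivity analysis that assumes higher risk in them.

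Decisions about treatment stay with the investigator, and no withdrawal reason needs to be deleted. The cost is amendment wording and occasional remote contacts or record checks. No new procedure is added.

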19.3 Early termination of clinical study

Both the Sponsor and Investigator reserve the right to terminate the clinical study at any time.

20 PUBLICATION POLICY

The results of the clinical investigation will be submitted, whether positive or negative for publication.

A 'Publication Agreement' will be signed between the Principal Investigator and the Sponsor (if applicable).

If such a Publication Agreement is not signed by both parties as a separate agreement but as part of an overall Clinical Trial Agreement, the publication policy should be part of such a Clinical Trial Agreement.

For more information on publication guidelines, please refer to the International Committee of Medical Journal Editors (ICMJE) on www.icmje.org.

